2.4 CLINICAL EXPERIENCE

SRA737 had not been administered to humans prior to the initiation of this study.

Several Chk1 and Chk1/2 inhibitors have however previously been investigated clinically. The development of several first generation inhibitors was terminated due to unfavorable pharmaceutical properties and/or unmanageable toxicities including off-target cardiovascular liabilities. Several second-generation Chk1 inhibitors are now in development.

LY2606368, an unselective Chk1/Chk2 inhibitor administered by intravenous infusion is currently the most advanced second-generation agent. This compound was the subject of 7 Phase 1 and 2 clinical studies both as monotherapy and in combination with various chemotherapeutic agents and radiotherapy as this current SRA737 study was activated. Interim data from a number of these studies suggests that (putatively on-target) myelosuppression including high-grade neutropenia, is dose-limiting. Favorable initial activity has also been noted with a PR rate of 38% in a study of 13 patients with HGSOC ([Lee 2016](#)).

GDC-0575, an orally available Chk1 inhibitor, is also currently being investigated in a Phase 1 clinical trial in refractory solid tumors and lymphoma. Data from this study had not been reported at the time of activation of this current SRA737 study.

The proposed trial design for SRA737 as a monotherapy is consistent with several previous studies of Chk1 inhibitors. Based on the limited existing clinical data from second-generation clinical programs, myelosuppression may be anticipated to occur in the clinical trial of SRA737 as a monotherapy.

Further information on SRA737 is available in the current version of the Investigator's Brochure.

2.5 RATIONALE FOR THE PROPOSED TRIAL

Although progress has been made in many areas of clinical oncology, the treatment options for patients with cancer remain limited and continue to represent an area of high unmet medical need. In the continually evolving science of cancer drug development, the ability to select patients for treatment based on relevant underlying genetic components of their disease provides a means for improving the potential for patient benefit without increasing overall risk.

Consistent with this paradigm, this clinical trial has been designed to define the RP2D for SRA737, while also evaluating which patients are most likely to benefit from treatment. Specific cohort expansion indications have been selected as being most likely to represent potential areas for SRA737 monotherapy efficacy, and the diagnostic test will be explored as a means to identify patients with greatest likelihood of benefit from treatment.

2.6 Benefit-Risk Assessment

SRA737 is a highly selective, orally bioavailable small molecule inhibitor of Chk1, a central regulator of the DDR network. In cancer cells, replication stress induced by oncogenes (eg, MYC and RAS oncogenes) combined with loss of function in tumor suppressors (eg, TP53) results in persistent DNA damage and genomic instability, a trigger of the DDR network.

Targeted inhibition of the remaining components of the DDR network such as Chk1 by SRA737 may be synthetically lethal to cancer cells and thus may have utility as a monotherapy in a range of tumor indications particularly in tumors with high rates of replication stress and genomic instability.

A body of experimental data supports the exploration of SRA737 as a single agent particularly in a molecularly-defined population. This first-in-human dose escalation study will be enriched in dose expansion cohorts with prospectively-selected genetically-defined subjects in tumor types that are known to have a high prevalence of genomic aberrations hypothesized to sensitize the tumor to Chk1 inhibition. Prospective selection of patients most likely to derive benefit from SRA737 will provide data to support the selection of specific indications and inform refinement of patient selection strategies in further clinical development. The indications for the expansion cohorts have been selected both on the scientific hypothesis of greater likelihood for benefit, as well as the high unmet medical need in these populations where alternative therapies are required.

Recent non-clinical toxicology data generated in the monkey, the most representative species for toxicity assessment of SRA737, indicate favorable tolerability at daily oral doses of 20 mg/kg, where mean C_{max} and AUC values reached 3.2 $\mu\text{g}/\text{mL}$ ($\approx 8 \mu\text{M}$) and 24 $\mu\text{g} \cdot \text{h}/\text{mL}$ ($\approx 65 \mu\text{M} \cdot \text{h}$), respectively. In contrast, clinical C_{max} and AUC values of 1.1 $\mu\text{g}/\text{mL}$ and 9 $\mu\text{g} \cdot \text{h}/\text{mL}$ were observed in the 600mg clinical dosing cohort ($n=1$), indicating a favorable exposure safety margin with considerable opportunity for ongoing dose escalation during the clinical study.

The likely target organs for SRA737 toxicity are the bone marrow and the GIT, both of which will be closely monitored in the ongoing study. Although no significant nonclinical cardiac liabilities have been observed in the benchmark non-rodent toxicity studies, cardiovascular safety assessments are included in this Phase 1/2 clinical study as a precaution. The rationale for the starting dose and schedule of SRA737, based initially on preclinical data, is provided in Section 2.3.7.

During the conduct of the study, the sponsor is committed to perform ongoing review of safety data with careful oversight of the subject's safety by the Cohort Review Committee. The protocol includes guidelines for the reduction, interruption and discontinuation of study treatment in the event of adverse events (AEs, Section 5.4).

Based on the non-clinical and clinical information currently available, the balance between anticipated efficacy/benefits and the potential safety risks for SRA737 remains highly favorable.

3 TRIAL DESIGN

3.1 CLINICAL TRIAL OBJECTIVES AND ENDPOINTS

3.1.1 PRIMARY OBJECTIVES AND ENDPOINTS

Primary objectives	Endpoints
To establish the safety profile of SRA737	Safety parameters (referencing National Cancer Institute – Common Terminology Criteria for Adverse Events [NCI-CTCAE] v4.03) including: incidence, seriousness, severity and causality of each AE to SRA737, timing of AE onset, AE duration, and AEs leading to interruption, modification, or discontinuation of study treatment, and primary reason for discontinuation of study treatment if other than disease progression (PD), laboratory (eg, clinical chemistry, hematology, urinalysis) and vital sign data
To determine the MTD with 1 or more schedules of administration of SRA737	The highest dose at which $\leq 33\%$ of subjects have a dose limiting toxicity (DLT) in a cohort of up to 6 subjects
To propose a recommended Phase 2 dose and schedule of SRA737	A safe and well tolerated dose and schedule that provides high exposure, based on all available PK, PDn, and safety parameter data from all cycles of therapy
To evaluate the preliminary efficacy of SRA737 including efficacy in prospectively-selected genetically-defined subjects enrolled into indication-specific expansion cohorts	Objective response rate (ORR) Disease control rate (DCR) Time to response (TTR) Duration of response (DOR) Progression-free survival (PFS) Time to progression (TTP) Overall survival (OS)

3.1.2 SECONDARY OBJECTIVES AND ENDPOINTS

Secondary objectives	Endpoints
To characterize the pharmacokinetic profile of SRA737	Plasma concentration-time profile based on PK parameters including, but not limited to: AUC_{inf} , AUC_{tau} , C_{max} , C_{min} , T_{max} , and $t_{1/2}$
To assess the relationship between response and the presence of selected genetic alterations detected in tumor tissue and/or circulating tumor deoxyribonucleic acid (ctDNA)	ORR and gene alterations in tumor tissue or ctDNA at baseline as measured by next generation sequencing (NGS)

3.1.3 EXPLORATORY OBJECTIVES AND ENDPOINTS

Exploratory objectives	Endpoints
To investigate the pharmacodynamics of SRA737 in tumor tissue	Proof of target engagement and changes in mechanism of action biomarkers between baseline and on treatment with SRA737, including, but not limited to: pSer296 Chk1, pS317 Chk1 and total Chk1
To investigate the pharmacodynamics of SRA737 in surrogate tissues such as blood or peripheral blood mononuclear cell (PBMCs)	Proof of target engagement and changes in mechanism of action biomarkers between baseline and on treatment with SRA737, including but not limited to: pS317 Chk1, pS345 Chk1, total Chk1, gammaH2AX and RAD51
To explore possible clinical predictors of outcomes	Characteristics such as performance status, prior therapy, indication and other known or potential prognostic or predictive factors
To explore the relationship between exposure (PK) and QT/QTc, other electrocardiogram (ECG) parameters and cardiovascular safety findings	Association of QT, QTc, blood pressure (BP), heart rate, other ECG intervals with time-matched PK concentrations. Profile of QTc over the dosing interval

3.2 DESIGN OF THE CLINICAL TRIAL

This is a multicenter, first-in-human, Phase 1/2, open-label, dose-escalation trial in subjects with advanced solid tumors or non-Hodgkin lymphoma (NHL), with cohort-expansion phase in 6 indication-specific expansion cohorts (Figure 6). The trial will consist of 2 stages:

- Stage 1: A Dose Escalation Phase.

It is expected that between 30 and 50 subjects with solid tumors or NHL will be enrolled in the Dose Escalation Phase of the study.

Intensive PK and ECG monitoring for QTc assessments will be collected from all enrolled subjects, beginning with sampling before and after a single dose of SRA737 given on one day between Day -7 and Day -4. Tissue (archival or fresh) and blood will be collected for retrospective biomarker analyses.

Cohorts consisting initially of a single subject will receive escalating doses of SRA737, starting in Cohort 1 with 20 mg/day administered orally on a continuous daily dosing schedule in 28-day cycles. The dose will be escalated until the MTD has been identified, unless determined otherwise by the Sponsor in consultation with the Chief Investigator, for example, if an alternative schedule is pursued instead.

Once a SRA737-related, Grade 2 toxicity is observed in a dose escalation cohort during Cycle 1, that cohort will be expanded to 3 to 6 subjects, and subsequent dose level cohorts will follow a rolling 6 design. See Section 3.3 for additional details.

Dose escalation with an alternative schedule may begin at any time and may either run in parallel or instead of continued escalations in the continuous schedule.

The final number of subjects enrolled into the trial is dependent on the number of dose levels explored in the Dose Escalation Phase.

- Stage 2: A Cohort Expansion Phase.

Approximately 120 subjects will be enrolled into the Cohort Expansion Phase which consists of 6 indication-specific expansion cohorts of approximately 20 prospectively-selected genetically-defined subjects each (namely, subjects with previously treated metastatic CRC, HGSOC without *CCNE1* gene amplification, HGSOC with *CCNE1* gene amplification (or alternative genetic alteration with similar functional effect), mCRPC, advanced NSCLC, and HNSCC/SCC). This allows for a preliminary exploration of the efficacy of SRA737.

Intensive PK and ECG monitoring for QTc assessments will be performed for subjects in the Cohort Expansion Phase. However, the Sponsor may reduce or modify the requirements for PK sampling, including elimination or modification of the Day -7 to Day -4 visit, once sufficient data to evaluate the PK of SRA737 have been collected and analyzed. If this occurs, the modified requirements will be documented by an update to the appropriate study documents.

Tissue (archival or fresh) and blood will be collected for prospective genetic analyses to determine eligibility. See Section 7 for more details.

Prospective determination of tumor genetics to determine eligibility of subjects within the selected indications may begin prior to the completion of dose escalation.

Enrollment to the Dose Escalation and Expansion Cohorts may occur in parallel. A subject that qualifies for the Cohort Expansion Phase will be enrolled into an Escalation Cohort whenever possible. Any such subject will be considered to have enrolled in both phases simultaneously. Only when a dose escalation enrollment slot is not available for an eligible prospectively-selected genetically-defined subject, that subject may be enrolled to an expansion cohort and treated with SRA737 at the highest dose level previously determined to be safe. Intra-subject dose escalation is allowed for these, and for all, study subjects when a higher dose level has been determined to be safe in a cohort of Dose Escalation subjects.

[figure not shown]
Enrollment into the Expansion Cohorts requires that each subject's tumor has evidence of a combination of mutations which are expected to confer sensitivity to

Chk1 inhibition. Eligibility will be determined by the Sponsor's review of genetic abnormalities listed in Appendix 6.

Figure 6 Study Design

Dose escalation increments will be determined by cohort review process.

The dose of SRA737 will be doubled in subsequent cohorts until a subject in any cohort experiences a SRA737-related or probably related NCI CTCAE \geq Grade 2 toxicity; cohorts will then be expanded to 3-6 subjects following a rolling 6 design for that and subsequent cohorts, and, in the absence of a DLT, the dose of SRA737 will be escalated in less than 100% increments (typically 25-75% increments).

DLT = dose-limiting toxicity, NCI CTCAE = National Cancer Institute Common Terminology Criteria for Adverse Events, TBD = to be determined, MTD = maximum tolerated dose

3.3 DOSE ESCALATION PHASE

The Dose Escalation Phase will begin with an accelerated titration design which allows for single subject cohorts and 100% dose escalation increments if the previous dose level is determined to be safe by the cohort review process. The dose of SRA737 will be doubled in subsequent cohorts until a subject in any cohort experiences a SRA737-related or probably related National Cancer Institute – Common Terminology Criteria for Adverse Events (NCI-CTCAE) Grade 2 or greater toxicity during Cycle 1; cohorts will then be expanded to 3 to 6 subjects following a rolling 6 design for that and subsequent cohorts. In the absence of a DLT, the dose of SRA737 will be escalated in less than 100% (typically 25–75%) increments. The extent of the dose increase will be informed by the Cohort Review Committee.

Once the first subject in each rolling 6 cohort has completed an observation period of 7 days of continuous dosing (Days 1–7 inclusive), or a similar duration of observation on an alternative schedule, subsequent subjects may start treatment unless the Sponsor determines that safety findings in the first subject in that cohort warrants other action. With the exception of the single subject cohorts, a minimum of three evaluable subjects must have completed one cycle in order to decide to escalate the SRA737 dose. The minimum possible time between dose escalation cohorts is therefore 5 weeks.

Subjects who receive less than 75% of their planned doses in Cycle 1 for reasons other than SRA737-related toxicity will not be evaluable for assessment of DLT for dose review decisions and may be replaced in the cohort. Safety information for these subjects will, however, be considered to guide the extent of the dose increase.

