Study design (cont'd):	
Once a SRA737-related, Grade 2 toxicity is observed in a dose escalation cohort during Cycle 1, that cohort will be expanded to 3 to 6 subjects, and subsequent dose level cohorts will follow a rolling 6 design (see Section 3.3 for additional details). Dose escalation with an alternative schedule may begin at any time and may either run either in parallel or instead of continued escalations in the continuous schedule. The final number of subjects enrolled into the trial is dependent on the number of dose levels explored in the Dose Escalation Phase. Patients who are not evaluable for assessment of dose limiting toxicity (DLT) may be replaced.
 
Stage 2: A Cohort Expansion Phase
 
The Cohort Expansion Phase consists of 6 indication-specific expansion cohorts of approximately 20 prospectively-selected genetically-defined subjects each (namely, subjects with previously treated metastatic colorectal cancer [CRC], high grade serous ovarian cancer [HGSOC] without CCNE1 gene amplification, HGSOC with CCNE1 gene amplification (or alternative genetic alteration with similar functional effect), metastatic castration-resistant prostate cancer [mCRPC], advanced non-small cell lung cancer [NSCLC], and squamous cell carcinoma of the head and neck [HNSCC] or squamous cell carcinoma of the anus [SCCA]). This allows for a preliminary exploration of the efficacy of SRA737.
 
The goal of the expansion cohorts is to assess SRA737 across multiple tumor types in subjects who have a range of genomic profiles of interest as described in inclusion criterion 9. The Sponsor may choose to refine or select particular genomic profile requirements in each (or all) Expansion Cohort(s) based on observations of tumor response and clinical benefit in the ongoing study and/or other emerging clinical and nonclinical data. The Sponsor may also choose to select for alternative genomic profiles in the event profile(s) not associated with tumor responses are over-represented in subjects already enrolled.
 
Intensive PK and ECG monitoring for QTc assessments will be collected until the Sponsor determines sufficient data have been collected and analyzed across the study as a whole. Tissue (archival or fresh) and blood will be collected for prospective genetic analysis to determine eligibility. See Section 7.1.1 for more details.
 
Prospective screening of subjects within the selected indications to determine eligibility based on tumor genetics will begin prior to the completion of dose escalation. Eligibility will be determined by the Sponsor's review of genetic abnormalities detected in genes in the categories listed in inclusion criterion 9. Enrollment to Dose Escalation and Expansion Cohorts may occur in parallel.
 
A subject that qualifies for the Cohort Expansion Phase will be enrolled into a Dose Escalation Cohort whenever possible. Any such subject will be considered to have enrolled in both phases simultaneously. Only when a dose escalation enrollment slot is not available for an eligible genetically-defined subject, that subject may be enrolled to an expansion cohort and treated with SRA737 at the highest dose level previously determined to be safe. Intra-subject dose escalation is allowed for these, and for all, study subjects.

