3.4 DEFINITION OF DOSE LIMITING TOXICITY

The DLT window is defined from the first Day -7 to Day -4 dose until the end of Cycle 1 (up to 35 days).

A DLT is defined as any highly probably or probably SRA737-related event of:

- Grade 4 neutropenia or thrombocytopenia that lasts for > 7 days despite withholding dosing and/or providing supportive care (eg, hematopoietic growth factors)

Note: In the event of a Grade 4 neutropenia or Grade 4 thrombocytopenia, a full blood count must be performed at least on Day 7 after the onset of the event to determine if a DLT has occurred. The investigator must continue to monitor the subject closely until resolution to ≤ Grade 3.

- Febrile Neutropenia
- A ≥ Grade 3 thrombocytopenia with ≥ Grade 3 bleeding
- A ≥ Grade 3 nonhematological toxicity with the following possible exceptions per Cohort Review discussion:
 - Alopecia of any grade
 - Grade 3 or 4 nausea or vomiting in subjects that have not received optimal treatment with anti-emetics
 - Grade 3 or 4 diarrhea in subjects that have not received optimal treatment with anti-diarrheal medication
 - Transient, asymptomatic Grade 3 biochemical abnormalities if agreed by the Medical Monitor and the Chief Investigator
 - Grade 3 fatigue, unless there is an increase by at least 2 grades from baseline (classed as the grade prior to first dose)
- Inability to receive 75% of planned dose in the first cycle during the DLT window due to drug-related toxicity

DLTs defined above will be considered for the purposes of dose escalation decisions; however, should cumulative toxicity become apparent this will also be taken into consideration when determining either the next dose level or the RP2D(s).

All DLTs must be reported to the sponsor or sponsor's delegate within 24 hours of site staff becoming aware of the DLT, including any change made to the grade or causality of an AE that may alter its DLT status, as this may affect dose escalation decision making.

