7.1 PRE-ENROLLMENT EVALUATIONS

All required procedures must be performed only after obtaining informed consent unless the assessment was already performed within the allowable window as standard of care.

Details of all evaluations/investigations for enrolled subjects, including relevant dates, required by the protocol must be recorded in the medical records.

Please also refer to the tabulated Schedule of Events in Section 7.6.

7.1.1 *SCREENING EVALUATIONS: PRE-SCREENING AND WITHIN 28 DAYS PRIOR TO ADMINISTRATION OF SRA737*

Repeat dosing will begin on Day 1, but subjects will also receive a single dose between Day -7 and Day -4 for the purpose of PK analysis until the sponsor determines sufficient data to evaluate the PK of SRA737 have been collected and analyzed. If this occurs, the modified requirements will be documented by an update to the Laboratory Manual.

Existing results such as radiological measurements may be used even where these investigations were performed prior to the subject's provision of informed consent for the study if they were performed within the required time window.

The following will be performed/obtained as part of Pre-Screening (no time restriction):

- Written informed consent (as detailed in Section 12.3)
- Determination of HPV status either from the subject's medical records, or assessment by local laboratory (subjects with HNSCC or SCCA only).
- Submission of, or confirmation of availability of, suitable archival tumor tissue or fresh tumor tissue (such as with fine needle aspirate) for tumor profiling.
 - For subjects being considered for enrollment to the Dose Escalation Phase, confirmation of the availability of suitable (as defined below) archival tumor tissue or planning for the acquisition of fresh tumor tissue after enrollment and before the start of treatment for **retrospective** tumor profiling is required.

If the subject is enrolled, archival tissue should be requisitioned for submission by Cycle 1 Day 1.

- For subjects being considered for enrollment to the Cohort Expansion Phase, determination of tumor genetics (as confirmed by a validated method performed in a Central Laboratory selected by the sponsor) and MSI status (required for CRC subjects and other subjects if clinically relevant), will be used to determine eligibility for the Cohort Expansion Phase. Archival or fresh tumor tissue should be submitted for **prospective** testing at the Central Laboratory as early as possible.

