11.2.4 PK/QTC

Time-matched ECG measurements and PK samples will be collected after a single dose of SRA737 on Day -7 to Day -4 and during Cycle 1 (See Section 7.7 for the Schedule of Secondary and Exploratory Assessments).

A concentration-effect model will evaluate the relationship between plasma concentrations and the mean change from Baseline in QTcF for all subjects in the PK/QTC study.

Plasma concentrations of SRA737 will be determined using a validated bioanalytical method and summarized using descriptive statistics. Pharmacokinetic parameters, including but not limited to C_{min} , C_{max} , T_{max} , AUC, $t_{1/2}$, total body clearance, and apparent volume of distribution, will be determined using non-compartmental method(s). PK data generated from this study

may be used in conjunction with PK data from other clinical studies in future meta-analyses for population PK assessment. These data will be reported separately.

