### 9.3.2. Study Day and Duration

Study day is relative to the start date of the first treatment of the treatment phase. As stated above subjects may have the first dose for intensive PK purpose prior to the first treatment of the treatment phase. In such cases the study day will not align with the very first dose subjects received. It is set up this way to be consistent with the protocol “Day” definition and to avoid confusion in the listings when the study day is used. There is no study Day 0 defined.

- For an assessment that occurred on or after the study treatment:  
Study day = Date of assessment – date of first study treatment in treatment phase + 1
- For an assessment that occurred prior to the study treatment:  
Study day = Date of assessment – date of first study treatment in treatment phase

A duration between any two dates (such as AE duration) expressed in days will be calculated using the following conventions: Duration = later date – earlier date + 1.

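### The rule that ends single-subject dose doubling stops at Cycle 1 in Section 3.3 but has no time limit in the Figure 6 note, so a toxicity confined to the run-in dose trips one wording and not the other

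*Protocol*

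**What the plan says.** The escalation starts with one subject per cohort and 100% increments. A related toxicity then switches it to cohorts of 3 to 6 and smaller steps, typically 25 to 75%. The protocol states that switch in four places:

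- Section 3.3: "Grade 2 or greater toxicity during Cycle 1; cohorts will then be expanded to 3 to 6 subjects following a rolling 6 design".
- Synopsis, repeated in the Section 3.2 text: "Once a SRA737-related, Grade 2 toxicity is observed in a dose escalation cohort during Cycle 1, that cohort will be expanded". SAP Section 3.1 has the same sentence.
- Note to Figure 6 in Section 3.2: "Grade 2 toxicity; cohorts will then be expanded to 3-6 subjects following a rolling 6 design for that and subsequent cohorts". It applies at Grade 2 or above and sets no time limit.

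The DLT rule has its own window in Section 3.4: "The DLT window is defined from the first Day -7 to Day -4 dose until the end of Cycle 1 (up to 35 days").

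The run-in dose is described apart from Cycle 1. Section 7.1.1 says: "Repeat dosing will begin on Day 1, but subjects will also receive a single dose between Day -7 and Day -4". Section 11.2.4 says that matched ECG and PK samples "will be collected after a single dose of SRA737 on Day -7 to Day -4 and during Cycle 1".

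Section 3.3.2 opens by counting DLTs and other drug-related events at the current dose level. Its bulleted decisions, however, are introduced as applying to the rolling 6 cohorts and begin from data on three subjects.

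**The concern.** The run-in dose is a subject's first exposure at a new dose level. Under the literal wording of Section 3.3, a related Grade 2 or greater event in those days does not end doubling if it settles before Day 1. Under the Figure 6 note it does. The event could even be a DLT under Section 3.4, for example a probably related Grade 3 non-hematological toxicity outside the listed exceptions. The bullets in Section 3.3.2 do not say what one DLT in a one-subject cohort requires.

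At stake is whether the next step is fixed by rule (expand to 3 to 6 subjects, then increments below 100%) or left to judgement (possibly one more subject at twice the dose). A fixed trigger in a first-in-human study is there so that this step does not depend on judgement, and two sites reading different pages could expect different actions.

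**Working it through.** **1. Reproduce the plan's figure.** Inputs: 28-day cycles (Section 5.1), run-in dose on Day -7 to Day -4 (Section 3.4), and SAP Section 9.3.2: "There is no study Day 0 defined". With no Day 0, a Day -7 dose falls 7 days before Day 1 and a Day -4 dose 4 days before.

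- Longest window: 7 + 28 = 35 days, which matches Section 3.4.
- Shortest window: 4 + 28 = 32 days.

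The 35 days are reached only if the run-in lies outside the 28 days of Cycle 1. Sections 7.1.1 and 11.2.4 agree with that reading.

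**2. Apply each wording to a related Grade 2 or greater event in a single-subject cohort.**

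| Event | Section 3.3 trigger | Figure 6 note | Within the 3.4 window |
|---|---|---|---|
| Run-in only, below Grade 2 before Day 1 | not met | met | yes |
| Run-in, still Grade 2 or more in Cycle 1 | met | met | yes |
| First seen in Cycle 1 | met | met | yes |
| First seen in Cycle 2 or later | not met | met | no |

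The first row is the safety gap. The last row is the same inconsistency at the other end. The second row assumes that an event still present in Cycle 1 counts as occurring in it.

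A subject who stops before Day 1 because of the drug is caught separately. Section 3.4 counts as a DLT "Inability to receive 75% of planned dose in the first cycle during the DLT window due to drug-related toxicity", and Section 3.8.1 keeps such a subject evaluable. A subject who stops for another reason is not evaluable and may be replaced (Section 3.3).

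**3. Size of the uncovered period, continuous schedule.**

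- Share of the DLT window: 4/32 = 12.5% to 7/35 = 20%.
- Share of planned doses: 1/(1 + 28) = 1/29 = 3.4%.

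Neither is the probability of a missed trigger; the documents give no event rate.

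**4. Consequence if review did clear the dose and double it.**

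- Against a 75% increment: 2.00/1.75 = 1.14 times the dose.
- Against a 25% increment: 2.00/1.25 = 1.60 times the dose.
- Subjects forgone at the current level: 3 - 1 = 2 to 6 - 1 = 5.

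**The case against.** The strongest reply is that the governing text is clear and the safeguards are adequate. The synopsis, Section 3.2, Section 3.3 and the SAP agree; only a figure note differs, and that note itself leaves increments to cohort review. Section 3.3 allows doubling only if review finds the previous dose safe. Section 3.3.1 puts all adverse events before the review and makes DLTs the primary consideration. Section 3.4 says DLTs in its window, run-in included, will be considered in escalation decisions, and requires them to be reported within 24 hours.

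The subject must also go on to complete an evaluable Cycle 1, meaning at least 0.75 x 28 = 21 daily doses on the continuous schedule, with no further related Grade 2 or greater toxicity. That is rechallenge evidence. After a Grade 3 or greater related non-hematological event, Table 2 in Section 5.4.1 also suggests considering interruption and resumption at a lower level; a subject so reduced would hardly support doubling from the original dose. The gap disappears if the sponsor drops the run-in visit, as Section 7.2.1 permits.

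Most of this stands and limits the practical risk. It does not remove the contradiction. If the figure note is the slip, the less protective wording governs, and one DLT in a single-subject cohort still has no stated action in the Section 3.3.2 bullets.

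A reader might infer more than the documents support:

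- That the Grade 2 trigger and the DLT window must coincide. Nothing requires it: one changes cohort size and increment, the other governs stopping. Aligning them is sensible, not obligatory.
- That a particular jump, such as 160 to 320 mg, is at risk. Section 2.6 already reports exposure from a 600 mg cohort (n=1), so escalation had passed that step. Nor is 600 mg on the strict doubling ladder from 20 mg (20, 40, 80, 160, 320, 640).

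**Conclusion.** The inconsistency is real and minor. The fixed rule in Section 3.3 omits a related Grade 2 or greater event, DLTs included, that follows the run-in dose and drops below Grade 2 before Day 1; the Figure 6 note covers it. In that case a further doubling rests on cohort review rather than on a rule. It does not follow that doubling would happen, or that a run-in DLT would be ignored.

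The uncovered period is 4 to 7 days. The dose ratio of 1.14 to 1.60 applies only if review sees the event and still doubles. No sample size, analysis or stated figure is affected.

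The conclusion assumes that Cycle 1 starts on Day 1, that the run-in dose is still given, and that single-subject cohorts are still in use. The documents do not say whether doubling was continuing at the time of Version 8.0.

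**What to change.** In the synopsis, Section 3.2, Section 3.3 and the Figure 6 note, define the trigger in identical words as related Grade 2 or greater toxicity from the first dose of SRA737, including any Day -7 to Day -4 dose, to the end of Cycle 1. This closes the run-in gap and settles the open upper end of the figure note; cumulative toxicity in later cycles remains a matter for cohort review under Section 3.3.1. In Section 3.3.2, add that a DLT in a single-subject cohort expands that cohort under the rolling 6 rules. SAP Section 3.1 can follow for consistency; it drives no dosing or analysis.

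The cost is wording in five protocol places and one SAP sentence. No new data are needed, because adverse events are already recorded from the first dose (Section 7.2.1). An earlier switch to multi-subject cohorts might add 2 to 5 subjects at one dose level.
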